Chervinsky, et al^[19] reported a 60% failure rate for a similar group of patients receiving placebo, so we assume that $\theta_A = 0.60$. Greening, et al^[8] reported a 5% failure rate for a similar group of patients receiving salmeterol and ICS, so we assume that $\theta_B = 0.05$. Although it is anticipated that $\theta_A > \theta_C > \theta_B$, there is no report in the literature as to an anticipated failure rate for Group C. As such, a rate which would be considered clinically significant was discussed at length by the ACRN Steering Committee. The committee agreed that a reduction in the treatment failure rate of Group A by more than 50% would be clearly clinically relevant in this patient population. Therefore, failure rates less than 30% were assumed for Group C in order to calculate the sample size. The Steering Committee also recognized that the eventual choice of a precise failure rate for Group C needed to reflect the relative numbers of asthmatic patients with moderate asthma within the entire asthmatic population in the United States (approximately 25% of the total) in order to set realistic recruitment goals for this disease severity category. After numerous discussions with input from various individuals, the Steering Committee agreed that a 20% treatment failure rate for Group C would be the best choice to address both the clinical

relevance of any observed differences and the patient population disease severity restraints.

It is not of interest to detect failure rates in the other direction, i.e., $\theta_B > \theta_C > \theta_A$, so one-sided tests are used. One interim analysis is planned for this trial when approximately one-half of the randomized patients have completed the trial. Therefore, a significance level of $\alpha = 0.029$ (see Pocock^[18]) will be invoked at each analysis. Using $\beta = 0.20$ (80% statistical power) and allowing for a 10% withdrawal rate, a total of 130 randomized patients are needed in Groups B and C. In order to perform the secondary comparison of Group B versus Group A, the target sample size for Group A will be 20 randomized patients. This comparison of Group C versus Group A will have 80% statistical power based on the assumed failure rates of 20% and 60%, respectively. Thus, the required sample size for this trial is 150 randomized patients.

XI. REFERENCES CITED

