II. BACKGROUND AND RATIONALE

A. Introduction

In developing protocols to ascertain the relative safety of chronic beta agonist therapy in moderate asthma, members of the ACRN Steering Committee were concerned that the group of asthmatic patients who could be considered to have moderate disease were too heterogeneous to construct a single study that would yield meaningful information for all within this group. Indeed, many patients with moderate disease are adequately controlled with inhaled corticosteroid (ICS) doses $\leq 400 \mu\text{g}/\text{day}$, whereas others require higher doses of ICS with additional bronchodilator support in the form of sustained released theophylline or long acting inhaled or oral β -agonists. Further, pulmonary function as measured using either spirometry or peak flow meters may vary widely both from an inter and inpatient standpoint. Thus, to safely address questions regarding the proper placement of chronic bronchodilator therapy in asthma, more than one protocol appeared to be required.

To this end, the Steering Committee focused their efforts on designing two studies that would share a common run in phase, but permit the randomization of the patients into two separate protocols based on both levels of pulmonary function measured acutely as well as their stability following six weeks of ICS therapy. These two protocols have been given the acronyms **SOCS** (salmeterol *off* corticosteroids) and **SLIC** (salmeterol \pm inhaled corticosteroids). Patients whose disease activity was more on the mild end of the moderate category would be entered into the SOCS protocol, whereas patients whose disease activity was more on the moderate to severe end of the moderate category would be enrolled in the SLIC protocol presented herein.

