This will be a 24 week, randomized, double-blind, prospective multi-center trial evaluating the ability of salmeterol to permit a stepwise reduction in inhaled corticosteroids in patients with moderate asthma. All patients with moderate asthma who meet the inclusion and exclusion criteria will receive both a methacholine bronchoprovocation (if baseline FEV₁ ≥ 55% predicted) followed by a sputum induction with hypertonic saline (if post-albuterol FEV₁ > 60% predicted). They will then be treated for a six week run-in period with a uniform dose of ICS (triamcinolone acetonide 400 µg BID) and prn use of the intermediate acting β₂-agonist, albuterol. Beginning with the run-in period, subjects will record in a daily diary their daytime and nighttime symptoms (dyspnea, wheeze, cough, each scored 0-3), AM and PM PEFs, albuterol use, and intercurrent illnesses and hospitalizations. At the end of the run-in period, patients will be randomized within either the SOCS or SLIC protocol based on FEV₁ measurements at the week six visit, and the stability of their PEF measurements during the preceding two weeks. (See diagram, page 24) Patients with greater airflow limitation (FEV₁ ≤ 80% predicted), or greater pulmonary function instability (variability > 20% but FEV₁ > 80% predicted), will be selected for the SLIC protocol. At the end of the six-week run-in period, patients will be randomized in a 2:13 ratio to placebo BID (Group A) and salmeterol 42 µg BID (Group B/C), respectively, for a period of two weeks. At the end of week eight, patients in Group B/C will be classified into subgroup I (FEV₁ > 80% and PEF variability over previous two weeks ≤ 20%) and subgroup II [FEV₁ ≤ 80% predicted or (FEV₁ > 80% predicted and PEF variability over previous two weeks > 20%)]. Then a stratified randomization will take place within each subgroup such that patients in Group B/C will be randomized to Group C (a two step dose reduction/elimination in ICS if they meet safety criteria) (800 – 400 µg at week 8, and 400 – 0 µg at week 16), and Group B (a sham stepwise reduction). All patients in Group A will also undergo a two step dose reduction identical to Group C. After qualifying for SLIC, all patients will receive 2 puffs of salmeterol (42µg) (single blind); one hour later, if their FEV₁ ≥ 55% predicted, methacholine bronchoprovocation will be performed. They will visit the clinical center every 2-4 weeks for an interval history and physical examination, diary review, quality of life measurements, and spirometry (see detailed schematic). At all subsequent visits patients in Groups A, B and C will receive 2 puffs of salmeterol (single blind) and, at designated visits, this will be followed one hour later by methacholine bronchoprovocation if their baseline FEV₁ ≥ 55% predicted. Sputum induction for analysis of markers of inflammation will not be performed at any subsequent visit. Patients will be assigned treatment failure status if their pulmonary function, beta agonist use, or symptom control significantly worsens as defined by a set of strict criteria. If this occurs prior to the scheduled end of the study, the patients may be rescued using a steroid burst algorithm, while at the same time increasing their dose of triamcinolone acetonide to the baseline dose of 800 µg/day. The patients will continue to be followed and all scheduled visits and testing will occur but no further inhaled corticosteroid dose reductions will be attempted. Patients will continue to take their study salmeterol (or placebo) unless the physician can document that treatment failure status was causally related to taking this medication. Glaxo, Inc. has kindly agreed to supply active and placebo canisters for albuterol (Ventolin[®]) and salmeterol xinafoate (Serevent[®]), and Rhône-Poulenc Rorer has graciously consented to supply active and placebo canisters for triamcinolone acetonide (Azmacort[®]) to be used in this protocol.

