If the prebronchodilator FEV₁ value at Visit 5 or later is $\leq 80\%$ of the PREbronchodilator value obtained at Visit 4, the patient should be given albuterol (≥ 6 puffs in one hour) to assess the degree of reversibility in his/her airflow obstruction. These values must be reported to the physician responsible for the care of the ACRN patient on that day. If the physician determines that the subject's response to the bronchodilator is satisfactory, and the patient's clinical condition is stable, the patient may continue in the study, provided he/she returns to the ACRN study site in 24-96 hours for repeat spirometry. In addition, the clinic coordinator or designee shall telephone the patient every 24 hrs to assess his/her condition. Prior to leaving the clinic, the patient should receive the usual doses of his/her study medications; no additional procedures scheduled for that study day shall be performed. At the additionally scheduled visit within the next 4 days, the repeat spirometric PREbronchodilator FEV₁ value must be $> 80\%$ of PREbronchodilator value obtained at Visit 4; if not, the patient will be considered a treatment failure at that time. If spirometric values are within the acceptable range, all procedures for the previously scheduled visit shall be performed according to the MOP and the patient will continue on his/her study medications.

Additional Treatment Failure Criteria:

1. Any use of oral or parenteral corticosteroids related to the treatment of the patient's asthma.
2. Occurrence of a significant exacerbation during the double-blind period.
3. Need for emergency treatment at a medical facility that is related to, or complicated by, the patient's asthma and which results in corticosteroid treatment or hospitalization for an acute asthma exacerbation.
4. Physician clinical judgment for safety reasons.

G. Criteria for Inhaled Corticosteroid Dose Reduction

1. The inhaled corticosteroid dose will be reduced from 800 to 400 μg at visit 5 and from 400 to 0 μg on visit 7, unless the patient has met the criteria for treatment failure status on the day of their visit or in the interval since their last visit.

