2. If patients meet criteria for treatment failure status, their dose of inhaled corticosteroids will be increased to the dose they were receiving at visit 4 (800 $\mu\text{g}/\text{day}$) delivered by an open-label inhaler. Study inhalers of corticosteroids (or its placebo) will be returned to the clinical center. If they meet the criteria detailed in Section VI, they will be treated with appropriate rescue algorithms for an asthma exacerbation. Study inhalers of salmeterol (or placebo) will be continued unless the physician can document that treatment failure status was causally related to taking this medication. They will continue to participate in the study until its termination (intent-to-treat analysis), but no further reductions in inhaled corticosteroid dose will be attempted during this time period. For safety reasons, all subjects will be seen within one week ($\pm 3\text{d}$) from the day they were categorized as achieving treatment failure status. Following this "safety" visit, subsequent protocol visits will continue in accordance with the visit schedule established at Visit 1 (see SOCS/SLIC MOP for details concerning possible replacement of scheduled protocol visits with treatment failure related visits).

IV. OUTCOME VARIABLES

The primary outcome variable will be the time to treatment failure. It will be evaluated using a Kaplan-Meier survival analysis. Secondary outcome indicators will include comparisons of FEV₁, mean peak flow variability (PM-AM peak flow difference normalized by the average of the AM and PM peak flow), methacholine airway responsiveness following premedication with salmeterol (evaluation of bronchoprotective effect), asthma symptom scores, quality of life, and rescue medication use at visits 5-11 to those obtained at visit 4.

Daily data obtained from post-randomization diary cards will be summarized and analyzed as averages. Because subjects are instructed to withhold their study salmeterol (or placebo) for 12 hours prior to a visit, the affected peak flow values will be excluded.

V. PROTOCOL

A. Subjects

1. **Sample size.** This trial has a target sample size of 150 randomized patients, with 20 in Group A, 65 in Group B, and 65 in Group C. See section X.F for the derivation of this sample size.

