Perform baseline spirometry and calculate PEF variability from diary cards
(If $FEV_1 > 80\%$ predicted)

If the patient continues to meet the inclusion criteria for the study, and fulfills the criteria for randomization, the ACRN DCC will be contacted and the patient will be randomized to either active salmeterol (13/15) (treatment Group B/C) or placebo salmeterol (2/15) (treatment Group A). Based upon this randomization, all patients will receive a coded, double-blind "regular use" inhaler to be taken twice a day (salmeterol or placebo). They will also receive two additional coded, double-blind inhalers to be taken twice daily at the same time the other blinded inhaler is taken. The inhalers will contain triamcinolone and the patients will be instructed to take two puffs of each inhaler twice daily. All patients will receive open label albuterol inhalers, to be used as needed for rescue treatment. Thus, each patient will receive a total of 4 inhalers. Prednisone tablets will also be provided. New diary cards will be issued. Based on data obtained in the previous two weeks, values for lower limits of acceptable peak flow measurements (prebronchodilator PEF < 65% of the mean value of AM prebronchodilator PEF recorded for the two weeks (weeks 5 and 6) prior to Visit 4 on any 2 of 3 consecutive scheduled measurements) will be calculated for each individual. They will be instructed to contact the study center immediately if peak flow measurements fall outside the acceptable range. They will also be instructed as to the level of rescue medication use which would be in excess of acceptable limits, and the need to contact the study center immediately if usage exceeds these limits. Patients will be asked to withhold their rescue inhaler for 6 hours and their salmeterol (or placebo) inhaler for at least 12 hours (to facilitate both AM and PM patient visits and to maximize the consistency of the time at which methacholine bronchoprovocation is performed in relationship to salmeterol dosing) prior to all future visits. Patients will be instructed to return to the clinical study center in 2 weeks.

Telephone Call, Week 7

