personnel will review the appropriateness of the timing of medication use, peak flow recording and symptom recording. All patients should have withheld their rescue inhaler for at least 6 hours and their salmeterol (or placebo) inhaler for at least 12 hours prior to the visit. Following baseline spirometry, all patients will receive 2 puffs of salmeterol (42 μ g) (single blind). One hour later, if the postbronchodilator FEV₁ \geq 55% predicted, methacholine bronchoprovocation will be performed. If the postbronchodilator FEV₁ $<$ 55% predicted, one attempt will be made to schedule the subject for retesting within the visit window, and the current visit will be stopped. If the subject cannot be rescheduled, all remaining visit procedures, with the exception of the methacholine bronchoprovocation, will be carried out and the visit completed. Guidelines for peak flow safety limits and rescue medication use will be reviewed. Patients will be randomized into their final study treatment groups. Those on active salmeterol at Visit 5 will be randomized to receive either the ICS reduction (Group C) or the sham reduction (Group B), whereas patients on placebo salmeterol at Visit 5 (Group A) will all undergo the ICS reduction. Patients in Group A will undergo a sham randomization in order to preserve all levels of blinding. Patients will receive two new coded, double-blind "steroid" inhalers to be taken 2 puffs twice daily. They will also receive a new "salmeterol" inhaler (placebo in Group A, active drug in Groups B and C) and will be further instructed to maintain at a dose of 2 puffs twice daily. Following methacholine bronchoprovocation, 2 puffs of albuterol will be administered. Open label albuterol will be issued as needed. Patients will be instructed to return to the clinical center in 2 weeks.

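### Secondary outcomes use one reference visit (Visit 4) for two randomizations; a change from Visit 4 within Group C cannot show that ICS reduction did no harm

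*Protocol*

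**What the plan says.** Section IV lists FEV₁, peak flow variability, methacholine responsiveness after salmeterol and other secondary outcomes, and compares "asthma symptom scores, quality of life, and rescue medication use at visits 5-11 to those obtained at visit 4". It does not say whether the comparison is within or between groups.

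The relevant events fall at two visits.

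- **Visit 4.** Patients are selected for SLIC: "Patients with greater airflow limitation (FEV₁ ≤ 80% predicted), or greater pulmonary function instability" (Section II, Protocol Overview). They are then randomized 13:2 to regular salmeterol (B/C) or placebo (A) (Section V.E, Visit 4).
- **Visit 5.** Groups B and C come into being: "Those on active salmeterol at Visit 5 will be randomized to receive either the ICS reduction (Group C) or the sham reduction (Group B") (Section V.E, Visit 5). The first ICS step is taken at the same visit: "The inhaled corticosteroid dose will be reduced from 800 to 400" µg, with the second step at Visit 7 (Section III.G).

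Section X.E counts the primary outcome after Visit 5. Aim 1 (Section II.B) concerns improvement on adding salmeterol, Aim 2 ICS reduction without deterioration, and Aim 3 bronchoprotection over time.

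**The concern.** Aim 2 asks what happens when ICS is reduced in patients already on salmeterol. Visit 4 precedes regular salmeterol, so a change measured from there starts one intervention too early. Visit 4 is also the visit whose FEV₁, with the preceding peak flow data, admits the patient, so later values tend to rise by regression to the mean in every arm. In Group C both effects run against an ICS loss and can cover it, which is the direction the hypothesis favours.

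The protocol itself expects movement between the two visits. The SLIC entry rule at Visit 4 is the same rule that defines Subgroup II at Visit 5 (Sections III.C and III.E). Subgroup I can arise only in patients who changed in between. The second randomization is stratified on that change, yet the reference visit for secondary outcomes ignores it.

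Visit 5 is also listed among the outcome visits. Its spirometry, quality of life, methacholine and diary data reflect the period before the first ICS step. For B versus C it is a baseline.

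**Working it through.** The protocol gives no figure for the secondary outcomes, so there is none to reproduce. The check uses FEV₁ in % predicted.

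**Inputs from the protocol.** Selection at Visit 4 on FEV₁ of 55-80% predicted (Section V.E); salmeterol in both B and C from Visit 4; 1:1 split at Visit 5; loss in C only; target numbers A 20, B 65, C 65 (Section V.A).

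**Assumed inputs.** Mean before selection 75 to 85; SD 14; between-visit correlation r of 0.7 to 0.9, equal for all pairs of visits; salmeterol gain g = 5 (also 0 and 8); ICS loss L = 5. Only the FEV₁ route into SLIC is modelled, not the peak flow variability route.

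**Expected changes to Visit 11**, with R the regression to the mean:

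- C from Visit 4: g + R - L; B from Visit 4: g + R; difference C - B: -L
- C from Visit 5: -L; B from Visit 5: 0; difference C - B: -L
- R = (1 - r) × (mean before selection - mean Visit 4 value of those selected)

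Worked case, mean 80 and r = 0.8: a normal distribution with SD 14 cut to 55-80 has mean 70.4, so R = 0.2 × 9.6 = 1.9. Group C from Visit 4: 5 + 1.9 - 5 = +1.9, although the true loss is 5.

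**Simulation results (L = 5 throughout):**

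| Mean, r, g | R | C from V4 | C from V5 | C - B from V4 | C - B from V5 | Residual SD adjusted for V4 | Residual SD adjusted for V5 |
|---|---|---|---|---|---|---|---|
| 75, 0.9, 5 | 0.57 | +0.55 | -5.02 | -5.02 | -5.02 | 6.10 | 5.84 |
| 80, 0.8, 5 | 1.92 | +1.91 | -5.01 | -5.01 | -5.02 | 8.41 | 7.92 |
| 85, 0.7, 5 | 4.06 | +4.07 | -4.99 | -5.00 | -4.99 | 9.99 | 9.41 |
| 80, 0.8, 0 | 1.92 | -3.06 | -4.99 | -5.00 | -5.02 | 8.39 | 7.91 |
| 80, 0.8, 8 | 1.93 | +4.94 | -5.00 | -4.99 | -5.01 | 8.41 | 7.93 |

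- Within C, the sign is wrong whenever g + R exceeds L. With no salmeterol gain, the loss is still understated (-3.1 instead of -5.0).
- Between C and B, both baselines recover -5.0 in every row.
- Precision: 1 - 5.84/6.10 = 4.3% and 1 - 7.92/8.41 = 5.8%; over all combinations run, about 4 to 6% lower residual SD with Visit 5 as covariate. The gain comes from covariate adjustment. Simple subtraction of Visit 5 gives none here: at mean 80 and r = 0.8, the SD of change is 8.50 from Visit 4 and 8.85 from Visit 5.

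**Precision of B+C versus A at Visit 5.** Standard error = √(1/130 + 1/20) = 0.240 SD. Detectable difference at 80% power, two-sided 5% (assumed, no losses): 2.8 × 0.240 = 0.67 SD unadjusted. With Visit 4 adjustment at r = 0.7: 0.67 × √(1 - 0.49) = 0.48 SD; at r = 0.9: 0.67 × √(1 - 0.81) = 0.29 SD.

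**The case against.** The strongest reply is that B and C were selected by the same rule, both took salmeterol from Visit 4, and were randomized afterwards. Salmeterol gain and regression to the mean then cancel. This stands in full. A reader might infer that a Visit 4 baseline hides a loss in B versus C; the design and the table both rule that out.

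Second, Section IV does not prescribe a within-group analysis. The rationale for Group A in Section V.G shows that group comparisons were in mind, and models are commonly left to an analysis plan. A missing model is indeed no finding. The reference visit, however, is fixed here, and so is the treatment of Visit 5 as an outcome.

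Third, comparing Visits 5-11 with Visit 4 includes Visit 5 against Visit 4, which supplies the data for Aim 1. True, but the randomized contrast is not named. It matters because Section V.G leaves out an arm on placebo salmeterol without taper and Group A tapers from Visit 5. Visit 5 is therefore the only outcome visit at which A and B+C have been on the same scheduled ICS dose.

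Fourth, the hypothesis in Section I can be read as a net question, for which the state before salmeterol is a natural reference. That is fair. But Research Question 2 asks about reduction after salmeterol has been started, and the net change still carries regression to the mean with no untapered placebo arm to remove it.

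Fifth, Visit 4 is needed elsewhere. Aim 3 requires it, and at that visit "After qualifying for SLIC, all patients will receive 2 puffs of salmeterol" before the methacholine test, so for bronchoprotection it is the proper first-dose reference. This stands, and the fix keeps it.

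A reader might also want secondary data cut at treatment failure, because patients then receive open-label ICS at the Visit 4 dose. The documents do not support that as a remedy: follow-up after failure is a stated intent-to-treat choice. On the assumed rates, cutting would remove about 20% of C against 5% of B, and those removed would be the patients doing worst.

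**Conclusion.** The point holds in a limited form. Section IV gives one reference visit where the design needs two. Change from Visit 4 within Group C is not evidence that ICS reduction was harmless: under the assumed inputs a 5-point loss shows as a gain of 0.6 to 4.1 points. The size depends on the assumed mean, SD, correlation and salmeterol gain, none of which the protocol gives; the structure g + R - L does not.

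For C versus B the choice of visit is a matter of precision only, about 4 to 6% in residual SD under equal correlations. It would be more if Visit 5 tracks later visits more closely than Visit 4 does. Importance is minor to moderate: secondary outcomes only, and the primary analysis already starts after Visit 5.

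**What to change.** Reword Section IV so that each question has its own contrast and baseline:

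- **ICS reduction (Aim 2):** C versus B, between groups, at Visits 6-11, adjusted for the Visit 5 value and Subgroup I/II.
- **Salmeterol (Aim 1):** B+C versus A at Visit 5, adjusted for the Visit 4 value, with a note that 20 patients in Group A limit its precision.
- **Change from Visit 4:** descriptive, and for loss of bronchoprotection (Aim 3). State that a within-group change from Visit 4 is not to be read as absence of an ICS-reduction effect.

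All the measurements are already scheduled at Visits 4 and 5. The cost is a paragraph of text and a few models. The main drawback is the wide interval for the Aim 1 contrast.

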
III. INCLUSION AND EXCLUSION CRITERIA

A. Inclusion Criteria (at visit 1)

1. Male and female subjects, between the ages of 12 and 65 years.
2. For patients not already taking inhaled corticosteroids:
 - a) $FEV_1 \leq 80\%$ of predicted.
 - b) Documentation from preceding 6 months of $\geq 12\%$ increase in FEV_1 after aerosolized albuterol.
3. For patients already taking inhaled corticosteroids:
 - a) $FEV_1 \geq 40\%$ of predicted.
 - b) If FEV_1 is 40-80% of predicted, patient must:
 - provide documentation from preceding 6 months of $\geq 12\%$ increase in FEV_1 after aerosolized albuterol
 - OR
 - document from the preceding 6 months or demonstrate a 20% reduction in FEV_1 in response to a concentration of inhaled methacholine ≤ 8 mg/ml ($PC_{20} FEV_1 \leq 8$ mg/ml).
 - c) If FEV_1 is $> 80\%$ of predicted, patient must document from preceding 6 months or demonstrate a 20% reduction in FEV_1 in response to a concentration of inhaled methacholine ≤ 8 mg/ml (i.e., $PC_{20}FEV_1 \leq 8$ mg/ml).
4. Ability to provide informed consent, as evidenced by signing a copy of the consent form approved by the Committee on Human Research of the study institution.
5. Non-smoker (total lifetime smoking history ≤ 10 pack - years; no smoking for at least 1 year).
6. No smokeless tobacco use for at least one year.

B. Exclusion Criteria (at Visit 1)

1. Use of any drugs listed in Table 1 during the designated washout period prior to Visit 1, or intention to take the drug during the study.

Table 1. Drugs to be withheld throughout the study	Washout prior to Visit 1
Inhaled Steroids, except as provided in study	None
Oral Steroids	≥ 6 weeks
Cromolyn/Nedocromil	≥ 6 weeks
Oral beta-adrenergic agonists	≥ 1 week
Monoamine oxidase inhibitors	≥ 4 weeks
Tricyclic antidepressants	≥ 4 weeks
Beta-adrenergic blockers	≥ 4 weeks
ACE inhibitors	≥ 4 weeks
Inhaled beta-adrenergic agonists (intermediate-acting, e.g., albuterol, terbutaline, metaproterenol, pirbuterol, bitolterol), except provided in study	≥ 8 hours
Salmeterol, except as provided in study	≥ 48 hours
Anticholinergics	≥ 48 hours
Short-acting theophylline (e.g., Slophyllin® tablets)	≥ 12 hours
Long-acting theophylline (e.g., Theo-Dur®, Slo-BID®)	≥ 24 hours
Ultra long-acting theophylline (e.g., Theo-24®, Uniphyt®)	≥ 48 hours
Antihistamines (except for Astemizole and Loratidine, see below)	≥ 72 hours
Astemizole, Loratidine	≥ 72 hours *
Zafirlukast (Accolate)	> 6 weeks
Zileuton (Zyflo)	> 6 weeks

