Drugs withheld prior to pulmonary function and/or methacholine challenge, per MOP	Specified time period
Albuterol	≥ 6 hours
Salmeterol Study Drug	≥ 12 hours
Terfenadine (Allegra)	≥ 48 hours
Chlorpheniramine (ChlorTrimeton)	> 48 hours
Methylxanthine-containing foods or beverages (e.g., coffee, tea)	≥ 8 hours
Alcohol-containing foods or beverages	≥ 8 hours

* Since these medications may remain in the body for weeks following administration, it is recommended that prick skin testing with histamine be performed in patients who are currently on treatment. If a flare ≥ 5mm develops following testing, the patient would be eligible for study participation. If not, the patient would need a longer washout period (possibly weeks) prior to retesting and enrollment.

2. Medication use: Chronic use of any medication other than β-agonists and inhaled corticosteroids, except oral contraceptives and other hormonal forms of contraceptives (i.e. DepoProvera®, Norplant®), estrogens/progesterone replacement therapy for post-menopausal women, vitamins, nasal beclomethasone (2 puffs each

nare, BID) at a stable dose throughout the entire study (see MOP), acetaminophen, non-steroidal anti-inflammatory medications (e.g., aspirin, naproxen, ibuprofen), thyroid replacement medications, terfenadine, anticholesterol medication, or medium and low potency topical cutaneous steroids.

Allowable medications also include:

- a. calcium supplements
- b. nasal saline spray
- c. topical eye preparations for allergic eye symptoms (e.g. antihistamines, NSAIDs, or antiallergic compounds)
- d. diuretics
- e. specific antihypertensives (e.g. calcium channel blockers, clonidine, etc.)
- f. antibiotics for acne
- g. stool softeners, psyllium
- h. acyclovir
- i. chlorpheniramine (48 hour washout)
- j. pseudoephedrine (48 hour washout)

3. Lung disease other than asthma.
4. Established diagnosis of vocal cord dysfunction.
5. Significant medical illness other than asthma.
6. History of respiratory tract infection within the previous 6 weeks.
7. History of a significant exacerbation of asthma in the previous 6 weeks (see section VI for definition of significant exacerbation and guidelines for treatment).
8. History of life-threatening asthma requiring treatment with intubation and mechanical ventilation within the past 10 years.
9. Hyposensitization therapy other than an established maintenance regimen.

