To date, we have screened well over 500 subjects for our database. Of those screened at the Moffitt-Long site, less than 10% are members of ethnic minorities. Over 60% of those screened at the Oakland satellite are of this category.

C. Drug Supplies

Drug supplies for this study will consist of the inhaled corticosteroid, triamcinolone acetonide (delivery of 100 μg /puff), to be supplied by Rhône-Poulenc Rorer, salmeterol xinate (21 μg /puff) and albuterol (90 μg /puff) to be supplied by Glaxo, Inc. Both companies will supply matching placebo canisters. The ACRN will contract with ProClinical, Inc. to work with the DCC to ensure proper blinding and coding of drugs (see Section X.B.). The participation of the pharmaceutical companies in this protocol is limited to the provision of drugs and placebos. They have not participated in the design of the study.

D. Compliance and Monitoring

In order to determine subject compliance with study drug usage, information recorded on subjects' diary cards regarding number of puffs taken from each inhaler each day will be reviewed at each visit. Limitations of this mechanism for monitoring compliance are accuracy of the subject's recall and honesty.

E. Visit Structure

Visit 0, Prescreening

Subjects will be interviewed prior to protocol entry (either by phone or in person) regarding their asthma and medical history. Specifically, the current status of asthma control, use of asthma and non-asthma medications, and health status in the previous 6 weeks will be determined. An overview of the goals of the study and the visit structure and procedures involved will be presented. If the patient appears to fulfill entry criteria, is interested in study participation, and is not taking oral corticosteroids or inhaled nedocromil or cromolyn, Visit 1 may be scheduled. If the patient is taking one of these asthma medications regularly, a pre-study visit must be scheduled, informed consent obtained, and the patient evaluated by the study investigator as to the appropriateness of drug withdrawal for the 6 weeks prior to Visit 1. If warranted, the investigator may request additional pre-study visits for evaluation of asthma stability during this 6 week period.

Visit 1, Week 0

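### The Visit 0 safeguard before drug withdrawal omits zafirlukast and zileuton, although Table 1 requires a washout of more than 6 weeks for both

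*Protocol*

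**What the plan says.** Visit 0 (section V.E) is a prescreening interview by telephone or in person. Visit 1 can be booked when the candidate seems eligible, is interested, and "is not taking oral corticosteroids or inhaled nedocromil or cromolyn, Visit 1 may be scheduled". For a candidate who takes one of those drugs regularly, "a pre-study visit must be scheduled, informed consent obtained, and the patient evaluated by the study investigator as to the appropriateness of drug withdrawal" over the 6 weeks before Visit 1. If there is reason to, "the investigator may request additional pre-study visits for evaluation of asthma stability during this 6 week period".

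Section III.B, exclusion 1, bars "Use of any drugs listed in Table 1 during the designated washout period prior to Visit 1". Table 1 then sets a washout of at least 6 weeks for oral steroids and for cromolyn/nedocromil, and of more than 6 weeks for zafirlukast and for zileuton. The last two drugs are mentioned nowhere else in the protocol.

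For everyone not on a drug named at Visit 0, section V.E places written informed consent at Visit 1.

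**The concern.** The protocol sets its own standard: when a candidate has to stop an asthma drug for about 6 weeks to qualify, consent and an investigator's judgment come first, and stability visits are available. It then applies that standard to only some of the drugs that meet the description.

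A candidate who stops zafirlukast or zileuton to qualify must be off it for more than 6 weeks by Visit 1, which is also when consent is first taken. The withdrawal would then have been made for the trial, but before consent and without a required medical review. The trial recruits from age 12, so some of these candidates could be adolescents. What is at stake is consent and the safety of candidates before enrollment, not the trial's inference.

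**Working it through.** No calculation applies. The check compares the Visit 0 list with each row of Table 1.

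**Step 1: sort the Table 1 rows by washout.** The part of the table with washouts before Visit 1 has 18 drug rows:

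| Washout before Visit 1 | Rows | Count |
|---|---|---|
| About 6 weeks | oral steroids; cromolyn/nedocromil; zafirlukast; zileuton | 4 |
| 4 weeks | monoamine oxidase inhibitors; tricyclics; beta-blockers; ACE inhibitors | 4 |
| 1 week | oral beta-agonists | 1 |
| 8 to 72 hours | inhaled beta-agonists (8 h); salmeterol (48 h); anticholinergics (48 h); short-acting (12 h), long-acting (24 h) and ultra long-acting (48 h) theophylline; antihistamines (72 h); astemizole/loratidine (72 h) | 8 |
| None | inhaled steroids | 1 |

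Check: 4 + 4 + 1 + 8 + 1 = 18.

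**Step 2: compare with the Visit 0 list.** All four rows at about 6 weeks are asthma drugs. Visit 0 names the drugs in two of them and omits the other two: 2/4 = 50% of rows. This counts rows, not patients. The omitted rows have washouts at least as long as the covered ones (more than 6 weeks against at least 6 weeks), and the text gives no reason for treating them differently.

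**Step 3: see whether the general eligibility condition at Visit 0 fills the gap.** Washouts count back from Visit 1, not from Visit 0. For 8 of the 18 rows the washout is 8 to 72 hours, for example "Inhaled beta-adrenergic agonists (intermediate-acting, e.g., albuterol, terbutaline, metaproterenol, pirbuterol, bitolterol". Current use of a Table 1 drug at Visit 0 therefore cannot by itself stop a later Visit 1 from being booked. In addition, Table 1 excludes the three named drugs in the same way, yet Visit 0 states them as a separate condition. If the general condition already covered current use of a washout drug, that separate condition would be redundant.

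**Step 4: see whether exclusion 2 of section III.B fills the gap.** It bars "Chronic use of any medication other than β-agonists and inhaled corticosteroids", with listed exceptions. None of the three named drugs is among those exceptions, yet Visit 0 gives their regular users a supervised way in. Exclusion 2 therefore cannot be what separates zafirlukast and zileuton from them.

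**Step 5: see whether exclusion 7 of section III.B fills the gap.** It bars anyone with a significant exacerbation in the 6 weeks before Visit 1. That keeps a candidate who worsened out of the trial. It gives that person no supervision during the washout.

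**The case against.** The strongest reply is that nothing in the protocol is contradicted. Zafirlukast and zileuton appear only as exclusions, and no text invites anyone to stop them. On this reading Visit 0 opens a supervised route for three named drugs, and current users of the other two are not candidates. The interview asks about asthma medication, so such a user should not pass straight to Visit 1. The Boston recruitment plan in section V.B gives theophylline, cromolyn and nedocromil as examples of additional asthma drugs, and no center mentions the other two. Nothing prevents an investigator from arranging a pre-study visit anyway, and Visit 1 presupposes verbal contact with an investigator or a representative. The cut-off could also be called arbitrary, since the 4-week rows and oral beta-agonists are not covered either.

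Parts of this stand. The protocol directs no withdrawal of these drugs, exclusion 1 would stop enrollment without a washout, and nothing shows that many candidates take them. The rest does not remove the gap. Steps 3 and 4 show that the eligibility wording does not separate these two drugs from the three named ones. The contact before Visit 1 concerns the trial's general aim and outline, not whether to withdraw a drug. An investigator's freedom to do more is not the requirement set for the named drugs. The cut-off follows the protocol's own pattern: the 4-week rows are not asthma drugs, and oral beta-agonists need only 1 week.

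**Conclusion.** The concern holds. The Visit 0 safeguard covers two of the four asthma-drug rows with a washout of about 6 weeks and leaves out zafirlukast and zileuton. The period that could pass before first consent, without required review, is somewhat over 6 weeks for each such candidate.

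The practical size is minor. The protocol does not give the share of candidates on these drugs, and it is probably small. The conclusion assumes that some candidates would stop one of them in order to qualify; if none would, the gap has no consequence. Randomization, alpha, power, endpoints and the primary analysis are unaffected. It is worth correcting because it concerns consent and safety and costs very little.

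**What to change.** In section V.E, Visit 0:

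- Add zafirlukast and zileuton to the drugs that rule out booking Visit 1 directly. The requirement for a pre-study visit, consent and investigator evaluation then applies to all four rows.
- Replace both references to 6 weeks (the withdrawal period, and the period for optional stability visits) with *the Table 1 washout period prior to Visit 1*. The fixed figure does not match the washout of more than 6 weeks for the two added drugs.

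No other row of Table 1 needs to change. The cost is a few words and one extra pre-study visit, of a type the protocol already has, for each candidate taking either drug. Sample size and visit schedule after enrollment stay as they are.
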